10.2 Dose adjustment criteria

The DSP-5423P dose can be increased or reduced by 20 mg/day at each adjustment within a range of 40 mg/day, 60 mg/day or 80 mg/day according to the following dose adjustment criteria. The DSP-5423 (tablet) dose can be increased or reduced by 4 mg/day at each adjustment within a range of 8 mg/day, 12 mg/day or 16 mg/day according to the following dose adjustment criteria.

Regulatory Assessment timing

- When the CGI-S score is between 4 and 7 and when no safety concerns arise, the DSP-5423P/DSP4323 (tablet) dose should be increased.
- When the CGI-S score is 3 or lower with no safety concerns and when the Investigator expects further efficacy of DSP-5423P/DSP4323 (tablet), the DSP-5423P/DSP4323 (tablet) dose can be increased.

As necessary

- When the Investigator considers a higher dose of DSP-5423P/DSP4323 (tablet) to be necessary due to insufficient efficacy, the DSP-5423P/DSP4323 (tablet) dose can be increased.
- When the Investigator considers a lower dose of DSP-5423P/DSP4323 (tablet) to be necessary due to the AEs, the DSP-5423P/DSP4323 (tablet) dose can be reduced.

PANSS and CGI-S should be evaluated before the dose adjustment at each unscheduled visit (Section 11.2 Efficacy Assessments). DIEPSS should be evaluated as well as PANSS and CGI-S when the DSP-5423P/DSP4323 (tablet) dose is reduced due to extrapyramidal symptoms (Section 11.3 Safety Assessments).

After the dose adjustment, the Investigator will record the reason for the dose adjustment in the CRFs. The DSP-5423P/DSP4323 (tablet) dose should not be changed for at least 1 week in principle, after the dose adjustment.

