12.2 Objective Findings

Clinically significant abnormal objective findings (eg, clinical laboratory value, ECG value, and physical examination observation) will also be recorded as AEs. When a clear diagnosis is available that explains the objective findings, this diagnosis will be recorded as the AE, and not the abnormal objective finding (eg, viral hepatitis will be recorded as the AE, not transaminase elevation). If a definite diagnosis is not available, then record the sign (eg, clinically significant elevation of transaminase levels) or symptom (eg, abdominal pain) as the AE.

Clinical laboratory test results will be reviewed by the Investigator. The Investigator must determine the clinical significance of all out of range values. Clinical laboratory test with possibly drug-related or clinically relevant abnormal values of uncertain causality may be repeated. Any abnormal values that persist should be followed at the discretion of the Investigator. Laboratory reports will be initialed and dated by the Investigator.

All ECG tracings at the study center and ECG over-read reports by the central ECG reader will be reviewed by the Investigator. The Investigator must determine the clinical significance of all

abnormal ECGs. An ECG with possibly drug-related or clinically relevant abnormal findings of uncertain causality may be repeated. Any abnormal ECGs that persist should be followed at the discretion of the Investigator. ECG tracings will be initialed and dated by the Investigator.

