8.5 Analysis Visit

Data of DSP-5423P treatment period is defined as the data captured on Day 1 through 7 days after the final application of DSP-5423P.

All data will be organized and analyzed according to the scheduled timing as outlined in Tables 1 and 2 Schedule of Assessments and according to the visit denoted in the CRFs. Unscheduled visits may not be used for any analysis unless otherwise specified. However, the data collected at the discontinuation visit within 7 days from the final application of study drug are mapped to the next scheduled visit of the actual discontinuation date. In listing, all data including unscheduled visit data should be presented.

1) CRF discontinuation visits in DSP-5423 (tablet) treatment period

Assessments and tests	Relative Day	Analysis Visit
PANSS, CGI-S, DIEPSS, body weight, body temperature, blood pressure, pulse rate	Tab-Day 1 to 11	Tab-W1, 2, 4, 6
	Tab-Day 12 to 18	Tab-W2, 4, 6
	Tab-Day 19 to 32	Tab-W4, 6
	Tab-Day 33 or later	Tab-W6
Laboratory test, ECG	Tab-Day 1 to 18	Tab-W2, 6
	Tab-Day 18 or later	Tab-W 6

The Tab-Day 1 is defined as the date of initial administration of DSP-5423 (tablet). CRF discontinuation visits in DSP-5423 (tablet) treatment period is defined as data on first non-missing (ex. no visit or results are missing) visit which meets all above requirements. Laboratory test and vital sign (body temperature, blood pressure, pulse rate) are performed visit handling for each item. Others are not considered as missing if they have any one component.

2) CRF discontinuation visits in DSP-5423P application period

Assessments and tests	Relative Day	Analysis Visit
PANSS, CGI-S, DIEPSS, C-SSRS,	Day 1 to 11	W1, 2, 4, 6, 8, 12, 16, 20, 24, 28, 36, 44, 52
	Day 12 to 18	W2, 4, 6, 8, 12, 16, 20, 24, 28, 36, 44, 52

Assessments and tests	Relative Day	Analysis Visit
Skin irritation assessment, body weight, body temperature, blood pressure, pulse rate	Day 19 to 32	W4, 6, 8, 12, 16, 20, 24, 28, 36, 44, 52
	Day 33 to 46	W6, 8, 12, 16, 20, 24, 28, 36, 44, 52
	Day 47 to 60	W8, 12, 16, 20, 24, 28, 36, 44, 52
	Day 61 to 92	W12, 16, 20, 24, 28, 36, 44, 52
	Day 93 to 120	W16, 20, 24, 28, 36, 44, 52
	Day 121 to 148	W20, 24, 28, 36, 44, 52
	Day 149 to 176	W24, 28, 36, 44, 52
	Day 177 to 204	W28, 36, 44, 52
	Day 205 to 267	W36, 44, 52
	Day 268 to 323	W44, 52
	Day 324 or later	W52
Laboratory test, ECG	Day 1 to 18	W2, 6, 12, 20, 28, 36, 44, 52
	Day 19 to 46	W6, 12, 20, 28, 36, 44, 52
	Day 47 to 92	W12, 20, 28, 36, 44, 52

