9.12.2 Laboratory test

Observed values and changes from baseline at DSP-5423P application period for the hematology, and blood chemistry parameters will be summarized by visits including LOCF endpoints. For urinalysis parameters, the number and percentage of subjects in each category of parameters will be summarized at baseline of DSP-5423P application period, each visit, and LOCF endpoint. All laboratory parameters and any abnormal laboratory values, which are all values beyond its own normal range at least one time whenever in DSP-5423P application period, will be listed respectively.

Criteria for Markedly Abnormal Post-Baseline Laboratory Values(MAPLV) for abnormal values in the hematology, and blood chemistry parameter can be found in Table 6. The frequencies and percentages of subjects who met MAPLV at least once in the post-baseline of DSP-5423P (including unscheduled visits), will be presented.

Table 6 Criteria for Markedly Abnormal Post-Baseline Laboratory Values

Hematology Parameter	Markedly Abnormal Range
Hemoglobin	Male: ≤ 11.5 g/dL
	Female: ≤ 9.5 g/dL
Hematocrit	Male: $\leq 37\%$
	Female: $\leq 32\%$
WBC	$\leq 2.8 \times 10^3/\mu\text{L}$
	$\geq 16 \times 10^3/\mu\text{L}$
Platelets	$\leq 75 \times 10^3/\mu\text{L}$
	$\geq 700 \times 10^3/\mu\text{L}$
Chemistry Parameter	Markedly Abnormal Range
ALT	$\geq 3 \times \text{ULN}$
AST	$\geq 3 \times \text{ULN}$
Alkaline Phosphatase	$\geq 1.5 \times \text{ULN}$
Na/Sodium	$\leq 130 \text{ mEq/L}$

	> 150 mEq/L
K/Potassium	< 3 mEq/L
	> 5.5 mEq/L
Cl/Chloride	< 90 mEq/L
	> 115 mEq/L
Blood Glucose (fasting)	< 50 mg/dL
	> 250 mg/dL
HbA1c	>= 7.5%
Total Bilirubin	> 2 x ULN
Blood Urea Nitrogen	> 30 mg/dL
Creatinine	> 2.0 mg/dL
CK	> 3 x ULN
Serum Prolactin	>= 5 x ULN
Triglycerides (fasting)	> 300 mg/dL
Total Cholesterol (fasting)	> 300 mg/dL

Note: A value is considered MAPLV if it is outside the Markedly Abnormal Range.

Note: Blood glucose, triglycerides, and total cholesterol are limited for blood samples collected in fasting state.

Box plot of observed value of the hematology and blood chemistry parameters will be provided by visits including baseline of DSP-5423P application period and LOCF endpoint.

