The number and percentage of subjects met have QTcB or QTcF criteria in Table 8 will be summarized. The ECG parameters for subjects who met the criteria in Table 8 at least once in the DSP-5423P post-baseline (including unscheduled visits) will be listed.

Table 8 QT Prolongation

QTc Prolongation
QTc > 450 msec
QTc > 480 msec
QTc > 500 msec
Increased from baseline > 30 msec
Increased from baseline > 60 msec

For DSP-5423(tablet) treatment period in Cohort 1, observed values and changes from baseline in DSP-5423(tablet) treatment period for the ECG parameters will be summarized by visits including LOCF endpoints.

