9.12.7 Skin irritation assessment

The number and percentages of subjects in each score of skin irritation assessment will be summarized by visits, baseline in DSP-5423P application period, each visit, LOCF endpoint, and also maximum score throughout the DSP-5423P post-baseline period. Skin irritation assessment scores will be listed.

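### The QTc threshold count, and less clearly the maximum skin score and C-SSRS period counts, do not lift the SAP's ban on unscheduled-visit data, and the protocol's DIEPSS highest-score table is missing from the SAP

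*SAP*

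**What the plan says.** SAP 8.5, and Protocol 15.3.10.2 in the same terms, state the general rule: "Unscheduled visits may not be used for any analysis unless otherwise specified". Listings are treated differently: "In listing, all data including unscheduled visit data should be presented".

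The safety sections of the SAP then differ in whether they depart from the rule.

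- **Laboratory, SAP 9.12.2:** an explicit departure. "The frequencies and percentages of subjects who met MAPLV at least once in the post-baseline of DSP-5423P (including unscheduled visits), will be presented".
- **Weight, SAP 9.12.3:** the count of subjects with a marked change carries the same parenthesis.
- **QTc, SAP 9.12.4:** "The number and percentage of subjects met have QTcB or QTcF criteria in Table 8 will be summarized". Nothing is said about unscheduled visits. The next sentence, on the listing of subjects who meet those criteria, does include them.
- **Skin irritation, SAP 9.12.7:** scores are tabulated by visit and "also maximum score throughout the DSP-5423P post-baseline period". Unscheduled visits are not mentioned.
- **C-SSRS, SAP 9.12.6:** counts are given for the entire patch period and for emergence after baseline. Unscheduled visits are not mentioned.
- **DIEPSS, SAP 9.12.5:** by-visit and LOCF summaries only. Protocol 15.3.6.2 also calls for a shift table, for each item, from baseline to each subject's highest score.

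Two protocol sections make off-schedule data foreseeable. Section 10.2, directly after a sentence on unscheduled visits, says: "DIEPSS should be evaluated as well as PANSS and CGI-S when the DSP-5423P/DSP4323 (tablet) dose is reduced due to extrapyramidal symptoms". Section 12.2 says: "An ECG with possibly drug-related or clinically relevant abnormal findings of uncertain causality may be repeated".

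**The concern.** Safety is the primary objective, and QTc, skin irritation, suicidality and DIEPSS scores are named safety endpoints. A patient seen between planned visits is often there because something is wrong. A rule that drops those visits from a maximum, or from a count of subjects who ever crossed a limit, therefore tends to remove bad values rather than a random sample, and such outputs can only move downward.

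The SAP recognises this for laboratory values and weight. Because it writes the exception out there, silence elsewhere reads as the default applying. Two programmers could defensibly produce different QTc, skin and C-SSRS tables from the same data.

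**Working it through.** The plan states no figure on this point, so there is none to reproduce. The check sets each output against the SAP 8.5 default.

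| Output | Exception written? | Result as written |
|---|---|---|
| Marked laboratory values (9.12.2) | Yes | Unscheduled data counted |
| Marked weight change (9.12.3) | Yes | Unscheduled data counted |
| QTc Table 8 count (9.12.4) | No | Default applies: not counted |
| QTc Table 8 listing (9.12.4) | Yes | Listed |
| Maximum skin score (9.12.7) | No, but taken over the whole post-baseline period | Ambiguous |
| C-SSRS entire-period and emergence counts (9.12.6) | No, but period-wide wording | Ambiguous |
| DIEPSS highest-score shift table (Protocol 15.3.6.2) | Table absent from SAP 9.12.5 | No worst-case output exists |

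**QTc.** A subject whose only QTc above 500 msec is on an unscheduled ECG is in the listing and not in the table. At a denominator of 200, the enrolment target, each such subject is worth 1/200 = 0.5 percentage points in the cohort total. How many there would be is unknown.

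**DIEPSS.** The table list in SAP 10.2 has four DIEPSS tables (14.3.7.1 to 14.3.7.4), covering total and symptom scores in each phase. None is titled as a shift or highest-score table. SAP section 3 nevertheless reports no change from the protocol.

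**How much the schedule alone can see (illustration only).** Assume a sign lasts D days and starts at a uniformly random time over 364 days. The chance that it is present on a nominal scheduled visit day is the sum over gaps of min(gap, D), divided by 364. Visit weeks come from SAP 8.5; the durations are my assumption, as the documents give none.

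- Skin, DIEPSS and C-SSRS: 13 visits, with gaps of 7 (×2), 14 (×3), 28 (×5) and 56 (×3) days.
  - D = 7: 13×7 = 91; 91/364 = 25%.
  - D = 14: 2×7 + 11×14 = 168; 168/364 = 46%.
  - D = 28: 2×7 + 3×14 + 8×28 = 280; 280/364 = 77%.
- ECG: 8 visits, with gaps of 14, 28, 42 and 56 (×5) days.
  - D = 7: 8×7 = 56; 56/364 = 15%.
  - D = 14: 8×14 = 112; 112/364 = 31%.
  - D = 28: 14 + 7×28 = 210; 210/364 = 58%.

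These figures ignore visit windows and the discontinuation visit, which SAP 8.5 maps to a scheduled visit. They show that scheduled visits can miss short-lived signs. They do not show how many missed signs would be measured at an unscheduled visit, which is the only quantity the rule affects.

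**The case against.** A reader might infer that reactions seen at unscheduled visits vanish from the safety results. The documents do not support that. TEAEs are defined by start date (Protocol 15.3.6.1, SAP 9.12.1), whatever the visit type. Extrapyramidal and application-site skin TEAEs have their own tables, clinically significant objective findings must be recorded as adverse events (Protocol 12.2), and all unscheduled data are listed. This stands, and it limits the point to scale- and threshold-based counts. It does not remove it: a QTc above 450 msec, a rise above 30 msec or faint erythema need not be judged clinically significant, so the scales and limits capture what event reporting may not.

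Skin and C-SSRS can be read as already inclusive. SAP 8.5 opens by defining patch-period data as everything from Day 1 to 7 days after the last application, the skin maximum runs throughout the period, and Protocol 15.3.6.5 counts suicidality occurring at least once. This too stands; these outputs are ambiguous, not clearly excluded. Nor do the documents require skin or C-SSRS ratings at unscheduled visits, so the amount of such data is unknown.

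For QTc, the intent was probably inclusive. Table 14.3.6.4 has a title parallel to the laboratory and vital-sign tables, and the listing includes unscheduled visits. One may therefore say that table and listing can disagree, not that they will. The repeat-ECG provision adds little: a repeat is optional, is not said to occur at an unscheduled visit, and may follow a scheduled tracing that is already counted.

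For DIEPSS, it would be wrong to say that a worst-case SAP output fails to lift the rule, since there is no such output. It is also too strong to say that an unscheduled rating enters no summary at all, because the LOCF definition in SAP 8.6 is not expressly limited to scheduled visits.

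**Conclusion.** The point holds in a limited form. It is firmest for the QTc Table 8 count: read as written, the default excludes unscheduled ECGs from the table while its companion listing includes them, and any resulting error is an undercount. For the maximum skin score and the C-SSRS period and emergence counts, the SAP is unclear and should say which reading applies. For DIEPSS, the defect is an undeclared omission of a protocol table, the one output that would have shown the worst ratings, provided it was allowed to use unscheduled visits.

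TEAE counts are unaffected. The size of the bias cannot be estimated from the documents. It depends on how many subjects have their worst value only at an unscheduled visit, and the overlap percentages above, which rest on assumed durations, do not measure that. The point matters because safety is the primary objective and the remedy is small.

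**What to change.** Before database lock, amend the SAP as follows.

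1. **9.12.4:** add *(including unscheduled visits)* to the Table 8 count, so that table and listing use the same data.
2. **9.12.7:** add the same phrase to the maximum skin score.
3. **9.12.6:** add it to the C-SSRS entire-period and emergence counts.
4. **9.12.5 and the table list in 10.2:** restore the baseline-to-highest-score DIEPSS shift table of Protocol 15.3.6.2 with the same phrase, so that ratings made at unscheduled dose reductions for extrapyramidal symptoms are used.
5. Keep all by-visit summaries on scheduled visits.

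The cost is a few words and minor programming. Whatever was recorded at unscheduled visits is already due to be listed, so no new data collection is needed. The downside is that some safety counts may become slightly less favourable.

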15.3.10.2 Analysis visit

All data will be organized and analyzed according to the scheduled timing as outlined in Table 2 and 3 Schedule of Assessments and according to the visit denoted in the CRFs. Unscheduled visits may not be used for any analysis unless otherwise specified. The data collected at the discontinuation visit within 7 days from the final application of study drug are mapped to the next scheduled visit of the actual discontinuation date and utilized for analysis.

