Visit window (Day)		-28~	-2~1	5~11	12~18	26~32	40~46	54~60	78~92	106~120	134~148	162~176	190~204	239~267	295~323	351~379	At discontinuation +5	6~17 days after completion of treatment or discontinuation
Obtaining informed consent	X																	
Patient demographics and medical history		X																
Dispense study drug			X ^{a)}	X	X	X	X	X	X	X	X	X	X	X	X			
Study treatment compliance				X	X	X	X	X	X	X	X	X	X	X	X	X		
PANSS		X	X ^{a)}	X	X	X	X	X	X	X	X	X	X	X	X	X ^{a)}	X ^{a)}	
CGI-S		X	X ^{a)}	X	X	X	X	X	X	X	X	X	X	X	X	X ^{a)}	X ^{a)}	
DIEPSS			X ^{a)}	X	X	X	X	X	X	X	X	X	X	X	X	X ^{a)}	X ^{a)}	
C-SSRS			X ^{a)}	X	X	X	X	X	X	X	X	X	X	X	X	X ^{a)}	X ^{a)}	
DAI-10			X ^{a)}				X						X			X	X	
EQ-5D			X ^{a)}				X						X			X	X	
Skin irritation assessment			X ^{a)}	X	X	X	X	X	X	X	X	X	X	X	X	X	X	
Laboratory test ^{b)}		X	X ^{a)}		X		X		X		X		X	X	X	X ^{a)}	X ^{a)}	
Pregnancy laboratory test ^{c)}		X														X	X	
12-lead ECG		X	X ^{a)}		X		X		X		X		X	X	X	X ^{a)}	X ^{a)}	
Body weight		X	X ^{a)}	X	X	X	X	X	X	X	X	X	X	X	X	X	X	
Body temperature, blood pressure, pulse rate		X	X ^{a)}	X	X	X	X	X	X	X	X	X	X	X	X	X	X	
Adverse event monitoring			←													→		
Blood sampling for PK							X						X			X	X	
Questionnaire																X	X	

a) The Day 1 is a DSP-5423P patch initiation/beginning Date.

b) Before the initiation/beginning of DSP-5423P attachment (Visit 2) and at the completion of the period of DSP-5423P attachment (Visit 113), perform should be performed at the in fasting state/conditions (End fast 10 hours before blood collection/drawing/sampling). Perform to in fasting state/conditions as much as possible in the rest of the Visit.

- c) Pregnancy only perform in premenopausal women available.
- d) Perform prior to initiation/beginning of attachment of the DSP-5423P. Prior therapy If antipsychotics are present, prior therapy after termination of antipsychotics, perform prior to initiation/beginning of DSP-5423P placement.
- e) Investigational drug except perform prior to administration initiation/beginning of antipsychotics.

5. Target sample size

Number of subjects enrolled: 200 subjects

- Number of subjects treated with DSP-5423P for 6 weeks and more in cohort 1: 50 subjects
- Number of subjects treated with DSP-5423P for 52 weeks in either cohort 1 or cohort 2: 100 subjects

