	Day 93 to 148	W20, 28, 36, 44, 52
	Day 149 to 204	W28, 36, 44, 52
	Day 205 to 267	W36, 44, 52
	Day 268 to 323	W44, 52
	Day 324 or later	W52
DAI-10, EQ-5D, Plasma drug concentration	Day 1 to 46	W2, 6, 12, 20, 28, 36, 44, 52
	Day 47 to 204	W28, 36, 44, 52
	Day 205 or later	W52

Day 1 is defined as the day of the initial application of DSP-5423P for each subject. CRF discontinuation visits in DSP-5423P treatment period is defined as data on first non-missing (ex. no visit or results are missing) visit which meets all above requirements. Laboratory test and vital sign (body temperature, blood pressure, pulse rate) are performed visit handling for each item. Others are not considered as missing if they have any one component.

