9.13.1 DAI-10

DAI-10 item scores will be summarized at baseline of DSP-5423P application period, each visit, and LOCF endpoints using number and percentage of subjects. For DAI-10 total score, the number and percentage of subjects and also descriptive summaries in change from baseline of DSP-5423P application period will be provided by each visit including LOCF endpoints. DAI-10 will be listed.

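### SAP 8.5 maps DAI-10, EQ-5D and plasma concentration data from early stoppers to visits at which the cohort 2 schedule does not collect them

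*SAP*

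**What the plan says.** SAP 8.5 states that data are "organized and analyzed according to the scheduled timing as outlined in Tables 1 and 2 Schedule of Assessments" and that "the data collected at the discontinuation visit within 7 days from the final application of study drug are mapped to the next scheduled visit". Protocol 15.3.10.2 has the same rule: such data are "mapped to the next scheduled visit of the actual discontinuation date". SAP section 3 declares no change from the protocol's analyses.

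SAP 8.5 then gives a mapping table for stops in the patch phase (item 2). The block for "DAI-10, EQ-5D, Plasma drug concentration" has three rows:

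- Day 1 to 46: "W2, 6, 12, 20, 28, 36, 44, 52"
- Day 47 to 204: Weeks 28, 36, 44, 52
- Day 205 or later: Week 52

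Below the table, the discontinuation record is defined as "data on first non-missing (ex. no visit or results are missing) visit which meets all above requirements".

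In the cohort 2 schedule (SAP 4.4, Table 2), DAI-10 and EQ-5D are marked at baseline, Weeks 6, 28, 52 and discontinuation. The row "Blood sampling for PK" is marked at Weeks 6, 28, 52 and discontinuation.

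The mapping feeds planned output. SAP 9.13.1 says DAI-10 total score summaries "will be provided by each visit including LOCF endpoints"; SAP 9.13.2 and 9.14.1 plan by-visit summaries of EQ-5D and plasma concentration.

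**The concern.** The text sends a discontinuation record to the next scheduled visit. The table offers visits at which the measure is not scheduled, and the placement sentence is too garbled to say which governs. Two programmers could produce different tables from the same plan.

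If the sentence means the first listed visit that has no data, every stop by Day 46 goes to Week 2. Nobody still on treatment has a Week 2 value for these measures, so that summary would consist of drop-outs only. Those same subjects would disappear from Week 6, which would then describe mainly the subjects who stayed on the patch. A subject who completed Week 28 and stopped by Day 204 would go to Week 36, which is also off-schedule for these measures. Following the table would also be an undeclared departure from protocol 15.3.10.2.

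**Working it through.** **1. Rebuild the table from the schedule.** Each row should run from the day after the previous scheduled visit's upper window limit to the upper limit of the next scheduled visit, and list that visit and the later scheduled ones. The inputs are the visit windows in SAP 4.4, Table 2: Week 6 is Day 40 to 46 and Week 28 is Day 190 to 204.

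This rule reproduces all 13 day ranges of the PANSS group and all 8 laboratory/ECG rows, both ranges and lists. For a Week 6/28/52 schedule it gives:

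| Days | Printed list | List implied by schedule | Off-schedule |
|---|---|---|---|
| 1 to 46 | 2, 6, 12, 20, 28, 36, 44, 52 | 6, 28, 52 | 5 of 8 (2, 12, 20, 36, 44) |
| 47 to 204 | 28, 36, 44, 52 | 28, 52 | 2 of 4 (36, 44) |
| 205 or later | 52 | 52 | 0 of 1 |

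The printed day limits 46 and 204 therefore fit Weeks 6, 28 and 52, while the first two lists do not.

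**2. Compare with the other blocks.** The PANSS group has 13 + 12 + ... + 1 = 91 entries and laboratory/ECG has 8 + 7 + ... + 1 = 36. None of these 127 is off-schedule for cohort 2. In the block at issue it is 5 + 2 + 0 = 7 of 13. The two faulty lists are identical to the laboratory/ECG lists for Day 1 to 18 and Day 149 to 204, which suggests copying.

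**3. Apply the table as printed, taking the first listed visit without data.**

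- Row 1: all 46 possible days map to Week 2. On 28 of them (Day 19 to 46) the Week 2 window, Day 12 to 18, has already closed. The corrected list gives Week 6, or Week 28 if Week 6 was already done.
- Row 2: Week 28 as intended, unless Week 28 was already done in its window and the subject stopped by Day 204. The record then goes to Week 36 instead of Week 52.
- Row 3: always Week 52.

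**4. Size if the table is followed.** Assume a share R of patch starters is still on treatment at Day 364 and the hazard is constant, so S(t) = R^(t/364). R = 0.5 is borrowed from protocol 15.1, where about half of enrolled subjects stopped early in the tablet studies. Protocol 13.2 allows up to 5 days between the last dose and the assessment.

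| Quantity | R = 0.5 | R = 0.4 | R = 0.6 |
|---|---|---|---|
| 1 − S(39): stopped before the Week 6 window opens | 0.072 | 0.094 | 0.053 |
| 1 − S(41): in row 1 even if assessed 5 days later | 0.075 | 0.098 | 0.056 |
| 1 − S(46): in row 1 if assessed on the day of stopping | 0.084 | 0.109 | 0.063 |
| S(190) − S(204): upper bound for Week 36 | 0.018 | 0.021 | 0.015 |

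At R = 0.5, 7.5% to 8.4% of starters are labelled Week 2 and 7.2% to 8.4% are missing from Week 6. At most 1.8% go to Week 36.

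**5. Illustration on DAI-10.** SAP 8.2 scores ten items 1 or −1, so the total runs from −10 to +10. If early stoppers differ from the others by 5 points (an assumption), dropping a share p of them moves the Week 6 mean by 5p: 5 × 0.0716 = 0.36 to 5 × 0.0839 = 0.42 points.

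**The case against.** The strongest reply is that the text and table need not conflict. The rule speaks of the next scheduled visit, not the next scheduled assessment, and Week 36 is a scheduled visit. Alternatively, the placement sentence requires a visit that satisfies all the preceding requirements, which could include the scheduled-timing rule; the surplus entries would then do nothing.

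The first reading fails on the table's own evidence. The laboratory/ECG block skips Weeks 1, 4 and 8, so the table maps by each assessment's own schedule, and the limits 46 and 204 fit that approach. It also cannot explain Week 2 as the target for a stop on Day 40. The second reading is possible, but the sentence is too unclear to rely on. What stands is that the harm is conditional on how the programmer reads it.

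Three further points stand:

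- The effect is limited to descriptive summaries, and discontinuation data would still appear in the listings.
- The size rests on stacked assumptions, including one hazard for both cohorts although cohort 1 reaches the patch after six weeks on tablets. The 5-point DAI-10 difference has no source in the documents.
- The count of 7 of 13 is for cohort 2. In the text copy available, the cohort 1 schedule columns do not line up, so its visits could not be confirmed. No cohort 1 row there shows a patch-phase Week 2 mark, and SAP Table 1 shows only three post-baseline marks each for DAI-10 and EQ-5D, which cannot match eight listed visits.

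**Conclusion.** The concern holds. For cohort 2, 7 of 13 visit entries in this block are off-schedule; that count needs no assumption. The consequence is conditional. If the table is followed, about 7 to 8 per 100 patch starters are labelled Week 2 and a similar number are missing from Week 6 (5 to 11 for 60% to 40% retention). This assumes a constant hazard and usable data from every early stopper; fewer usable records would shrink it. The Day 47 to 204 row matters only in a narrow case, at most 1.8% of starters (1.5% to 2.1% for 60% to 40% retention), because that bound takes every stop on Day 190 to 204 to follow a completed Week 28 visit.

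Only the by-visit DAI-10, EQ-5D and plasma concentration summaries are exposed. The primary safety results do not use this block, and Week 52 (LOCF) is defined separately in SAP 8.6. This should be corrected before programming; it does not threaten the study's conclusions.

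**What to change.** In the patch-phase mapping table of SAP 8.5, change the block to:

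- Day 1 to 46: Weeks 6, 28, 52
- Day 47 to 204: Weeks 28, 52
- Day 205 or later: Week 52 (unchanged)

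First check the cohort 1 DAI-10, EQ-5D and PK visits in the original schedule. Then reword the placement sentence to say that the record is assigned to the first listed visit with no data, once the sponsor confirms that this is the intent. The tablet-phase table in SAP 8.5 carries the same sentence and should be reworded identically.

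The cost is two table rows and one sentence, the latter in two places, before database lock. No new data or analyses are needed.
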